Providers who will be disclosing results to participants as part of the clinical trial must attend the in-person training or participate in a “make-up” training, consisting of watching recordings of didactic portions of the training and a virtual workshop/conference call with a HudsonAlpha GC to cover the discussion, hands-on, and role-play portions of the training.

The family-friendly report that will be developed for each case (by a HA genetic counselor) will also provide just-in-time education to the providers about a specific result and what it means – and provide a road map for topics to discuss with the participant.

If providers have questions regarding the study and specific results, they will be instructed to reach out to a HudsonAlpha GC for assistance, rather than their own site-specific GC. This will allow for centralized tracking and management of questions and issues that come up across all the sites and limit compromises to the clinical trial.

3.e.4 Study Outcomes

The **primary hypothesis for this non-inferiority trial** is that there will be no clinically relevant difference in parental empowerment, as a measure of health-related quality of life between parents in the Experimental (trained healthcare provider) arm when compared to the Standard of Care (genetics providers) arm. The primary study outcome is parental **empowerment** (McAllister *et. al.*, 2011, PMID: 21255005), which will be measured at the WGS return of results (ROR) visit, ~3 months after enrollment (see appendix 7 for survey measures). To ensure completion of the primary outcome, parents or caregivers will be asked to complete the parental empowerment measure on-site (or over the phone) immediately after the return of results. The remaining measures included in the ROR visit will be available to complete via Genome Gateway at their convenience.

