ENR: Enrollment * Post WGS (whole genome sequencing); [†]Genetic Counseling Outcome Scale; [‡]Parental Perceptions of Uncertainties in Genomic Sequencing; [◊]The Feelings About genomic Testing Results [#]Genetic Counseling Satisfaction Scale; [§]Genetic Knowledge Assessment; [¶]Visual Analog Scale ^Δ Parental Personal Utility Scale; [◊]Subjective Numeracy Scale; [¶]National Health and Nutrition Examination Survey; [□]12-Item Short Form Survey; [¶]Medical Outcomes Study. In green, primary analyses. ^{**} GCOS and FACToR need to be completed in-person (or over the phone) immediately after ROR delivery before leaving session.

(1) Primary Outcomes

The main outcome to be assessed as part of this randomized controlled clinical trial will be **parental empowerment** as measured at the main time point for our study (i.e., immediately after the ROR visit). Parental empowerment will be measured using the validated Genome Counseling Outcome Scale (GCOS), which contains 24, 7-point Likert type items, with higher scores representing greater empowerment. The GCOS-24 that we are using for our participants measures patient reported outcomes (PRO) and has been proposed as a measure to evaluate routine clinical genetics services (McAllister *et. al.*, 2011, PMID: 21255005).

(2) Secondary Outcomes

To avoid survey fatigue and undue emotional burden, not all secondary or exploratory outcome instruments will be administered at each time point. The secondary outcomes assessed at the main time point (WGS ROR visit) for this study are: **personal utility** and **parental uncertainty**. Personal utility will be assessed using the parental personal utility scale (PrU). Parental uncertainty will be assessed using the Parental Perceptions of Uncertainties in Genomic Sequencing (PUGS).

(3) Exploratory Outcomes

Genetic knowledge and background genetic education will be addressed using the Genetic Knowledge Assessment (Schmidlen et. al., 2016, PMID: 26306685). The Genetic Knowledge Assessment (GKA) is a questionnaire containing 15 true/false knowledge items and 4 education background questions. In addition, we will assess parental subjective understanding of their child's results by asking respondents to rate their agreement.

(4) Covariates

Beyond the primary, secondary, and exploratory outcomes described above, a schedule of other data being collected for use in various analyses is provided in table 2.

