Complete the Questionnaires assigned to you by selecting “My Surveys”

HUDSONALPHA
INSTITUTE FOR BIOTECHNOLOGY

Complete the Questionnaires assigned to you by clicking on a “Current Questionnaire” being sure to **reference the Study ID Number**

[figure not shown]
- Research nurse will complete assigned surveys in Genome Gateway.
 - These surveys are focused on phenotypes, previous genetic testing, prenatal testing (if known) and the enrollment process. (see screenshot steps below)
 - This information will be accessible to the analysis team at HudsonAlpha.

Select the patient from the list. Click Assign on Return of Results Baseline Questionnaire

[figure not shown]
Select due date from the calendar. Click Assign.
Reminders will be preset at defined times

- The due date should be up to ROR (roughly 2 ½ months for baseline). All subsequent surveys will be set 1-month from the day you assign the survey.
- The due date reminders will be automatically preselected for you (2-day before, 7-days before, and 14-days before)
- Research nurse will ship samples to the Clinical Services Laboratory at HudsonAlpha and submit them for sequencing via online portal.
- The research nurse will upload the W9 (needed for payment) and the informed consent form to GG.
 - Screenshots highlighting how to upload documents are below.

Uploading Documents to Genome Gateway

Navigate to “Files” from the homepage

To upload a file, select patient, then click “+”

Write message to send with file below

Choose File no file selected

1. Click "Choose File" - a finder window will open
 2. Select file (any file type) from correct location on computer
 3. Click "Choose"
 4. Click "Upload" to send it to the patient

**A message can be included with the file in the text box

- Forms/survey measures completed at enrollment
 - Informed Consent Form (ICF)- (paper form uploaded to Genome Gateway; hard copy kept in study binder)
 - W9 form (paper form uploaded to GG; hard copy kept in study binder until clinical trial team informs the coordinator to destroy- 7 years)
 - Participant Enrollment Survey
 - Sociodemographic in GG
 - Genetic Counseling Outcome Scale (GCOS)
 - Genetic Knowledge Assessment (GKA)
 - Visual Analog Scale (VAS)- Child's Health
 - Parental Perceptions of Uncertainties in Genomic Sequencing (PUGS)
 - Health Literacy
 - Subjective Numeracy Scale (SNS)
 - 12-item Short Form Survey (SF-12)
 - Medical Outcomes Survey (MOS)

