 - Genetic Counseling Outcome Scale (GCOS)
 - **This survey needs to be administered by the research nurse/coordinator after ROR. This is the primary outcome and needs to be completed directly after ROR.**
 - The Feelings About genomic Testing Results (FACToR)
 - **This survey needs to be administered by the research nurse/coordinator after ROR. This needs to be completed directly after ROR because it is an important covariate.**
 - Patient Assessment of Communication (Adapted from PACE) (Mazor et. al., 2016)
 - Visual Analog Scale (VAS)- Child's Health
 - Parental Perceptions of Uncertainties in Genomic Sequencing (PUGS)
 - Parental Personal Utility Scale (PrU)
 - 12-item Short Form Survey (SF-12)
 - Medical Outcomes Survey (MOS)
 - Understanding (Novel Measure)
- The research nurse/coordinator in partnership with HudsonAlpha will determine who the most appropriate clinical provider at each site is to receive the harmonized "provider survey." This provider should be the physician likely to make a clinical decision based on the WGS results at the time of ROR. If the neonate is inpatient this physician will likely be a neonatologist providing medical care for the neonate, if already discharged it could be pediatrician or another specialist depending on the neonate's symptoms. The site coordinator will determine the status of the proband (inpatient/outpatient) at the time of ROR (consulting with the family about this issue if already discharged) and will send the provider's name and contact information to [name], PhD ([contact]) within a week of

ROR appointment. Information can be sent via the Genome Gateway messaging tool. Information to be sent includes:

- Study ID
- Result type (positive/inconclusive/no finding)
- ROR date
- Clinical provider's name
- Clinical provider's contact information (email (required), phone, address)

(3) 1-month post-ROR Visit

- Forms/survey measures completed at 1-month post-ROR visit
 - Sociodemographic (if status has changed)
 - The Feelings About Genomic Testing Results (FACToR)
 - Patient Assessment of Communication (Adapted from PACE)
 - Visual Analog Scale (VAS)-Child's Health
 - 12-item Short Form Survey (SF-12)
 - Medical Outcomes Survey (MOS)
 - Understanding (Novel Measure)
 - Information Seeking

(4) 4-month post-ROR Visit

- Forms/survey measures completed at 4-month post-ROR visit
 - Sociodemographic (if status has changed)
 - The Feelings About Genomic Testing Results (FACToR)

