Form	Visit Administered	Instructions	Location
Informed Consent	Enrollment Visit	Participant/s reads consent. Study staff obtaining consent should sign, date, and time stamp	Paper, uploaded to Genome Gateway
Screening/Decliner Survey	Enrollment Visit	Completed by research nurse or study coordinator	Electronic Copy
Enrollment Survey	Enrollment Visit	Completed by parent or caregiver after study enrollment	Genome Gateway
Return of Results (ROR) Survey (In-clinic and At-home surveys)	GCOS and FACToR at ROR Visit; Additional measures after visit	Complete primary outcome measure (GCOS) and FACToR measure immediately after ROR, additional measures can be completed at participant's convenience	Genome Gateway
1-month post-ROR Survey	Complete 1-month post ROR	Complete survey online using GG	Genome Gateway
4-month post-ROR Survey	Complete 4-months post ROR	Complete survey online using GG	Genome Gateway
4-month plus 2 weeks post-ROR Survey	Complete 4-months plus 2 weeks post-ROR	Complete survey online using GG	Genome Gateway

User roles (researchers, providers, patients/participants and administrators) with secure log-in will be defined. The following information will be tracked: current user, database accessed, date, and time and the application will be stopped automatically after 15 minutes of user inactivity requiring a fresh log-in. All data will be collected via the questionnaires in Genome Gateway. The clinical trial study coordinator, clinical trial project manager and statistician will review all data collected weekly. This will help ensure all electronic forms are being completed correctly, are intact, and have been entered into system correctly.

3.j.2 General Instructions for Completing Forms

All data recorded in Genome Gateway will be maintained according to the International Council for Harmonization of Technical Requirements for Pharmaceuticals for Human Use (ICH) Good Clinical Practice (GCP) guidelines. Instructions for completing the questionnaires to ensure quality and consistency in data collection are below.

3.j.3 Retention of Study Documentation

Investigators will adhere to rigorous requirements and will retain copies of all paper (e.g. informed consent), electronic forms, and all other study documents for a period of no less than 7 years. Each site will maintain all documents, and at the close of the study UAB will retain all site documents.

3.j.4 Administrative Forms

Table 4. Administrative Forms

Form	Description	Location

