Appendix 15: **Return of Results Workflow**

SouthSeq Result Return Workflow for Site Coordinators

Return of Results for Cases randomized to Standard of Care Arm (GC disclosure)

Preparation

1. Receive message within [Genome Gateway](#) from HA genetic counselor that a case has results ready to be returned and has been randomized to GC disclosure. Message will include participant ID. Site GC will also receive this message.
2. Review result report, attached to the message sent in Genome Gateway. Reach out to HA genetic counselor with any questions or concerns.
3. Return of result visit gets scheduled with primary parent contact. Depending on site-specific procedures this could be done by the GC, site coordinator, or administrative support. Encourage in-person disclosure if possible. At this time, confirm that the participant's address has not changed. If it has, please update it in the demographics section of Genome Gateway and have them complete a new W9 form. The new W9 should be uploaded to the participants account and to the "Clinical Trial" account in Genome Gateway.

Disclosure (via phone)

1. Site genetic counselor will call the primary parent contact at the scheduled time.
2. RESULTS ARE DISCLOSED by the site genetic counselor.
3. Site genetic counselor will be in communication with you during the disclosure to let you know if they successfully connected with the family and when the conversation is finished.
4. Once result disclosure is in process, log into Genome Gateway and assign the "In-clinic Survey" and "At-Home Survey" to the participant.
5. Site genetic counselor will transfer the call to you when disclosure is over, if you are available. If you are not available at that time, call the primary parent contact back within the next 72 hours. Attempt to reach multiple times if no answer.
6. Over the phone, have primary parent contact complete the "In-clinic survey" by asking the questions and marking their response on a paper version of the survey. The paper survey should then be scanned and uploaded to the participant's account and to the Clinical Trial account. If the participants decide not to do the survey over the phone, please remind them to log into Genome Gateway to complete them and remind them that compensation will be provided for completed surveys.
7. Discuss next steps in SouthSeq for family to expect (see below "Next Steps" list).

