3. Return of result visit gets scheduled with primary parent contact. Depending on site specific procedures this could be done by the GC, site coordinator, or administrative support. Encourage in-person disclosure if possible. At this time, confirm that the participant’s address has not changed. If it has, please update it in the demographics section of Genome Gateway and have them complete a new W9 form. The new W9 should be uploaded to the participants account and to the “Clinical Trial” account in Genome Gateway.
4. Within NICU determine which provider will be doing the disclosure. Communicate this name to your HA genetic counselor when it is known. (This process will be site specific, once you have an established process, please send a description of that process to [name].)

Disclosure (via phone)

9. Disclosing NICU provider will call the primary parent contact at the scheduled time.
10. RESULTS ARE DISCLOSED by the NICU provider.

11. NICU provider will be in communication with you to let you know if they successfully connected with the family and when the conversation is finished.
12. Once result disclosure is in process, log into Genome Gateway and assign the “In-clinic Survey” and “At-Home Survey” to the participant.
13. NICU provider will transfer the call to you when disclosure is over, if you are available. If you are not available at that time, call the primary parent contact back within the next 72 hours. Attempt to reach multiple times if no answer.
14. Over the phone, have primary parent contact complete the “In-clinic survey” by asking the questions and marking their response on a paper version of the survey.
15. Discuss next steps in SouthSeq for family to expect (see below “Next Steps” list).
16. Find out if they remember their Genome Gateway username/password and website? If not, give it to them. If they don’t remember their password there is a link on the GG website they can click to re-set. (participants.southseq.org)

Disclosure (in-person)

7. Make sure disclosing provider has audio recording equipment (recorder with charge/batteries/available storage).
8. Make sure disclosing provider has a printed copy of the report to give to the family.
9. RESULTS ARE DISCLOSED by the NICU provider.
10. NICU provider will be in communication with you during the disclosure to let you know if the family showed up and when the conversation is finished.

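### The primary GCOS is meant to be completed before the family leaves the session, but the phone workflow allows later completion, one follow-up instruction differs by arm, and the SAP has no timing rule

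*Combined protocol and SAP*

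**What the plan says.** **Timing rule.** The footnote to Table 2 (Section 3.e.5) requires: "GCOS and FACToR need to be completed in-person (or over the phone) immediately after ROR delivery before leaving session". Section 3.f.2 (2), on the return-of-results (ROR) visit, says of GCOS: "This is the primary outcome and needs to be completed directly after ROR". Table 3 (Section 3.j.1) separates it from the rest: "Complete primary outcome measure (GCOS) and FACToR measure immediately after ROR, additional measures can be completed at participant's convenience". For the other ROR measures, including PUGS and PrU, Section 3.e.4 says: "The remaining measures included in the ROR visit will be available to complete via Genome Gateway at their convenience".

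**Phone workflow (Appendix 15, site coordinators).** In both arms, a coordinator who is not free when the disclosure ends is to "call the primary parent contact back within the next 72 hours" (step 5 in the standard-of-care list, step 13 in the experimental list). The in-clinic survey is then done over the phone "by asking the questions and marking their response on a paper version of the survey" (steps 6 and 14). Step 6 adds scanning and uploading, and then: "If the participants decide not to do the survey over the phone, please remind them to log into Genome Gateway to complete them", together with a reminder of payment. Step 14 has neither addition.

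**Online survey.** Both lists have the coordinator assign the in-clinic and at-home surveys in Genome Gateway during disclosure. Section 3.f.2 (1) sets the due date: "All subsequent surveys will be set 1-month from the day you assign the survey".

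**SAP.** It compares GCOS, PUGS and PrU means by arm with one-sided two-sample tests. It states no completion window, no rule for missing scores, and no analysis by delay or mode of completion.

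**The concern.** GCOS is placed at the end of the session so that it measures the disclosure itself. Two features of Appendix 15 loosen that.

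First, a score may be collected up to 72 hours later by phone, or online at any time up to the one-month due date. Section 3.e.3 (1) has learning topics matched to the result assigned after ROR, and the Next Steps list in Appendix 15 tells families to expect them within days. A late score can therefore reflect the disclosure plus that material. This applies to both arms.

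Second, the written effort to recover a score from a parent who declines the phone survey is greater in the genetic-counselor arm. If reluctant parents score lower, recovering more of them in that arm would lower its mean relative to the provider arm. That would shrink the counselor-minus-provider difference and favour non-inferiority. The documents do not show that this happened. The SAP as written gives no means of finding out.

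**Working it through.** **1. The two phone scripts side by side (Appendix 15).**

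| Element | Genetic-counselor arm | Provider arm |
|---|---|---|
| Surveys assigned in Genome Gateway during disclosure | Yes, step 4 | Yes, step 12 |
| Call-back within 72 hours | Yes, step 5 | Yes, step 13, same wording |
| Survey asked by phone, marked on paper | Yes, step 6 | Yes, step 14 |
| Scan and upload stated in the step | Yes, step 6 | No, but Section 3.f.2 (2) requires upload for any phone completion |
| Those who decline sent online, with payment reminder | Yes, step 6 | No |
| Next Steps list (online surveys, payment) | Yes, step 7 | Yes, step 15 |
| Help with log-in | Yes, step 8 | Yes, step 16 |

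The call-back conflicts with the timing rule but is the same in both arms. The only difference that bears on response is the instruction for those who decline.

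**2. The reported GCOS result.** Difference = 117.94 − 117.19 = 0.75. The reported upper limit is 4.83 and the margin is 10, so the slack is 10 − 4.83 = 5.17 points.

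The SAP passages give no analysed numbers. With equal arms, upper limit = 0.75 + t × √((13.85² + 14.86²)/n). At n = 96 per arm this is 4.84, and at n = 97 it is 4.82, so the stated 4.83 implies about 96 to 97 per arm. At n = 96 the test against 10 gives p ≈ 0.000007, consistent with the stated p < 0.0001.

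**3. Late completion.** Shift in the difference = excess share of late responders in one arm × mean change in score from answering late. Neither quantity is in the documents, so both are assumed:

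- 5% × 3 points = 0.15
- 10% × 5 points = 0.5
- 30% × 10 points = 3.0

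In the adverse direction the largest of these takes the upper limit to 4.83 + 3.0 = 7.83, still below 10. A shift above 0.75 could change the sign of the observed difference, but not the conclusion at this margin.

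**4. Differential non-response.** Let f be the extra share of provider-arm families missing from the analysis, and D the amount by which they would have scored lower. The bias is f × D, so reaching the margin needs D = 5.17/f, with the interval width held fixed. The pooled SD is √((13.85² + 14.86²)/2) = 14.36.

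| Assumed f | D needed (points) | In SDs |
|---|---|---|
| 10% | 51.7 | 3.6 |
| 20% | about 26 | 1.8 |
| 30% | 17.2 | 1.2 |
| 50% | 10.3 | 0.7 |

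The affected group is those who decline the survey among phone disclosures, and Section 3.f.2 (2) makes phone disclosure a last resort. An f large enough to matter is implausible from this instruction alone.

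**The case against.** The strongest reply is that the arms are in substance treated alike. Provider-arm families are assigned the same online survey and helped to log in. They also go through the same Next Steps list, which mentions surveys in Genome Gateway and payment. The missing sentence looks editorial: step 14 also lacks the upload instruction that applies to every phone survey, and its list is numbered 9 to 16 as if carried on from the other arm's 1 to 8. Most of this stands, and it limits the arm difference to one instruction. It does not answer the timing conflict, which is present in both arms, or the SAP's silence on it.

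Three stronger readings are tempting, and the documents do not support them.

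- A reader might infer that a provider-arm parent who declines the phone survey has no GCOS. Online completion remains open to that parent.
- A reader might infer that the step 6 difference could reverse the PrU result, whose upper limit of 10.13 is only 0.13 above its margin. Step 6 concerns the in-clinic survey, which by Table 3 holds GCOS and FACToR. PrU and PUGS are completed at the parent's convenience in both arms, with the same due date.
- A reader might infer that the 72-hour call-back itself favours one arm. Its wording is identical in both.

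**Conclusion.** The point holds as a cheap improvement. The timing rule for the primary outcome and the phone workflow disagree. One instruction for parents who decline the survey appears in only one arm's script. The SAP has neither a window nor an analysis that would show whether either matters.

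The overall GCOS conclusion at a margin of 10 is not expected to change. The slack is 5.17 points, against 0.15 to 3.0 for the assumed timing effects, and only large differential non-response would use it up. This rests on assumed shares and shifts, because the documents give neither the share of phone disclosures nor completion by arm. The effect within result-type strata cannot be computed, since the stratum means and numbers are not given in the SAP text.

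For PUGS and PrU the issue is variable timing by design in both arms. It calls for reporting, and is not evidence of an arm-specific bias.

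**What to change.** 1. Use one identical phone-survey step in both arm workflows of Appendix 15, including the upload instruction and the same handling of parents who decline.
2. State one GCOS window for both arms that reconciles the Table 2 footnote with the 72-hour call-back and the one-month due date.
3. Record the date and mode of completion: the interview date for phone or paper surveys (the upload date would be misleading), and the Genome Gateway timestamp for online ones.
4. Report GCOS completion, mode and days from ROR by arm, and add a sensitivity analysis restricted to same-day GCOS.
5. For PUGS and PrU, report days from ROR by arm and add a sensitivity analysis within a common window.

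The SAP already contains results, so items 4 and 5 are the immediate step, as far as completion dates were kept. Items 1 to 3 serve any remaining or future collection. The cost is a little extra record-keeping and analysis.
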